5.1 Recruitment and retention

The data to construct a CONSORT flow chart will be provided, as far as they are available in the study database. We will aim to tabulate: number of patients who were approached to participate in the study; number of patients who were excluded (with a tabulation of reasons for exclusion); number of patients who had the screening visit; number of patients who were excluded (with a tabulation of reasons for exclusion); number of patients who attended the baseline visit and received the

radioactive tracer [¹⁸F-fluoride]; number of patients who received the radioactive tracer and the baseline scan was not started, or started but aborted (with tabulation of reasons); number of patients who had baseline scan completed ; number of participants who withdrew consent including to use of existing data; number of participants with follow-up completed or who died, or had follow-up discontinued prematurely (with tabulation of reasons for premature discontinuation); ; total personyears of follow-up during the study, before Covid-19, and during Covid-19; number of participants included in analysis of primary outcome; number of participants excluded from analysis of primary outcome (with tabulation of reasons). Median, lower and upper quartile, minimum and maximum for duration of follow-up (overall and split by CMA status).

The statistical report will provide for the scanned population, not split by CMA status, a graph of cumulative number of patients recruited into the study over time and the dates the first and last patients were recruited; the number of study sites that recruited patients; a tabulation of the number of patients recruited by each study site.

5.2 Baseline characteristics

The following baseline characteristics will be tabulated by CMA status, and overall. No formal statistical testing will be performed.

Demographics

- a. Sex (Male/Female)
- b. Age (years) and (18-64, 65-84, ≥85)
- c. Body mass index (kg/m²)

Cardiovascular Risk Factors

- d. Smoking status (Never/Ex-smoker/Current)
- e. Hypertension or receiving treatment for hypertension (Yes/No)
- f. High cholesterol (>5 mmol/L) or on cholesterol lowering treatment prior to admission (Yes/No)
- g. Diabetes mellitus (Yes/No) if Yes then type (Type 1/Type 2)

Cardiovascular History

- h. Previous diagnosis of ischaemic heart disease prior to admission (Yes/No)
- i. Documented history of myocardial infarction prior to admission (Yes/No)
- j. Previous PCI prior to admission (Yes/No)
- k. Previous CABG (Yes/No)
- l. History of peripheral vascular disease in the medical notes (Yes/No)
- m. History of stroke or TIA in the medical notes (Yes/No)

Index Admission for Myocardial Infarction

- n. Index myocardial infarction (STEMI/NSTEMI)
- o. Coronary artery disease (Single vessel without LMS involvement, Single vessel with LMS involvement, Two vessels without LMS involvement, Two vessels with LMS involvement, Three vessels without LMS involvement, Three vessels with LMS involvement)
- p. Percutaneous coronary intervention (Yes/No)
- q. GRACE score (continuous)

Medication at Time of Screening Visit

N (%) of participants prescribed each of the following categories of medication:

- Aspirin P2Y₁₂ antagonist Statin
- Non-statin lipid lowering therapy
- Beta blocker ACE inhibitor or ARB Calcium channel blocker
 - Nitrate Other anti-anginal
- Mineralocorticoid receptor antagonist Other diuretic Anticoagulant
- Insulin
- Oral diabetic medication

5.3 Primary endpoint

5.3.1 Endpoint Definition

Cardiac death or non-fatal recurrent myocardial infarction or unscheduled coronary revascularisation between study entry and up to the end of follow-up. Unscheduled (late) coronary revascularisation is defined as revascularisation >6 weeks after screening visit date.

5.3.2 Primary Analysis

Table: N (%) of participants with primary outcome event by CMA status and overall.

Table: Numbers of participants whose first event was: a cardiac death, a non-fatal recurrent MI, or an unscheduled coronary revascularisation by CMA status and overall.

Figure: Kaplan-Meier estimates of cumulative incidence from analysis of time from study entry to first event of cardiac death or non-fatal recurrent MI or unscheduled coronary revascularisation by CMA status with p-value using a log-rank test. This will be the primary statistical analysis.

Participants who do not have a primary outcome event will be censored at the time of non-cardiac death or last follow-up.

Table: Hazard ratio of primary outcome by CMA status, with 95% CI, and associated p-value using Cox regression.

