4.3 EXCLUSION CRITERIA

Subjects will not enter the study if any of the following exclusion criteria are fulfilled:

1. Inability or unwilling to give informed consent
2. Women who are pregnant, breastfeeding or of child-bearing potential (women who have experienced menarche, are pre-menopausal and have not been sterilised) will not be enrolled into the trial
3. Major intercurrent illness with life expectancy <2 year
4. Renal dysfunction (estimated glomerular filtration rate ≤ 30 mL/min/1.73 m²)
5. Contraindication to iodinated contrast agent, positron emission tomography or computed tomography
6. Permanent or persistent atrial fibrillation
7. Previous screening as part of the trial

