10 STATISTICS AND DATA ANALYSIS

10.1 SAMPLE SIZE CALCULATION

Based on the assumption that one third of patients will have multiple 18Ffluoride positive plaques, and that the proportion of patients who have died or had a recurrent myocardial infarction by one year will be 30% in patients with multiple 18F-fluoride positive plaques, and 20% in other patients, we need 692 (231+461) subjects (power=80%, p= 2 sided 0.05). This proportion of events is

conservative, as we observed 20% deaths or recurrent myocardial infarctions at 1-year in consecutive unselected patients hospitalised with myocardial infarction [Mills et al, 2011; Mills et al, 2012]. In our preliminary data [Joshi et al, 2014], 25-45% of patients had untreated 18F-fluoride positive plaques. This calculation is from a continuity corrected chi-squared test. As the analysis will be time-to-event, we would expect to need 10% fewer patients, and therefore this calculation allows for 10% missing data.

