5.4 Secondary endpoints

5.4.1 All-cause death

Table: N (%) of participants with all cause death by CMA status and overall.

Figure: Kaplan-Meier estimates of cumulative incidence from analysis of time from study entry to death by CMA status with p-value using a log-rank test. Participants who do not have a relevant outcome event will be censored at the time of last follow-up.

Table: Hazard ratio of all cause death by CMA status, with 95% CI, and associated p-value using Cox regression.

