5.4.2 Cardiac death

Table: N (%) of participants with cardiac death by CMA status and overall.

Figure: Kaplan-Meier estimates of cumulative incidence from analysis of time from study entry to cardiac death by CMA status with p-value using a log-rank test. Participants who do not have a relevant outcome event will be censored at the time of non-cardiac death or last follow-up.

Table: Hazard ratio of cardiac death by CMA status, with 95% CI, and associated p-value using Cox regression.

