5.4.3 Non-fatal recurrent myocardial infarction

Table: N (%) of participants with non-fatal recurrent myocardial infarction by CMA status and overall.

Figure: Kaplan-Meier estimates of cumulative incidence from analysis of time from study entry to first non-fatal recurrent MI by CMA status with p-value using a log-rank test. Participants who do not have a relevant outcome event will be censored at the time of death or last follow-up.

Table: Hazard ratio of non-fatal recurrent myocardial infarction by CMA status, with 95% CI, and associated p-value using Cox regression.

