5.4.4 Unscheduled coronary revascularisation

Table: N (%) of participants with unscheduled coronary revascularisation by CMA status and overall.

Figure: Kaplan-Meier estimates of cumulative incidence from analysis of time from study entry to first unscheduled coronary revascularisation by CMA status with p-value using a log-rank test. Participants who do not have a relevant outcome event will be censored at the time of death or last follow-up.

Table: Hazard ratio of unscheduled coronary revascularisation by CMA status, with 95% CI, and associated p-value using Cox regression.

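### Four SAP figures present Kaplan-Meier estimates as cumulative incidence while censoring competing deaths, so they read at or above the true cumulative incidence (minor; tests and hazard ratios unaffected)

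*Combined protocol and SAP*

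**What the plan says.** SAP 5.3.2 specifies the primary figure as "Kaplan-Meier estimates of cumulative incidence from analysis of time from study entry to first event of cardiac death or non-fatal recurrent MI" or unscheduled revascularisation, by CMA status. Its censoring rule is: "Participants who do not have a primary outcome event will be censored at the time of non-cardiac death or last follow-up".

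Three secondary figures follow the same pattern:

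- **5.4.2, cardiac death:** "Kaplan-Meier estimates of cumulative incidence from analysis of time from study entry to cardiac death by CMA status", with non-cardiac death censored.
- **5.4.3, non-fatal recurrent MI:** the same label, with the rule "Participants who do not have a relevant outcome event will be censored at the time of death or last follow-up".
- **5.4.4, unscheduled revascularisation:** "Kaplan-Meier estimates of cumulative incidence from analysis of time from study entry to first unscheduled coronary revascularisation", with any death censored.

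The all-cause death figure in 5.4.1 also carries the label, but there "Participants who do not have a relevant outcome event will be censored at the time of last follow-up", and no competing death exists.

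Protocol 10.2.2, copied into SAP section 2, names Kaplan-Meier for the primary analysis and also censors non-cardiac deaths, but it describes the result as survival curves. The cumulative-incidence wording enters with the SAP's figure specifications. Neither document plans a competing-risks estimator.

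**The concern.** Cumulative incidence is the proportion of participants who have had the event by a given time. Kaplan-Meier treats a censored participant as still able to have the event at the same rate as those who remain at risk. That is reasonable for someone whose follow-up ends at study close and impossible for someone who has died. One minus Kaplan-Meier with competing deaths censored therefore describes a hypothetical setting in which those deaths do not occur, and it cannot fall below the actual cumulative incidence.

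What is at stake is the reported absolute risk. The primary objective in protocol 2.1.1 is an association, and the log-rank test and hazard ratio answer it. But these figures are the only planned display of risk at a given time by CMA status. The N (%) tables pool participants followed for very different lengths of time: about 2 to 6 years, from four years of recruitment plus two of follow-up (protocol 15.5), with contact continuing until the last participant's 2-year visit (7.2.3). If competing mortality differed by CMA status, the gap between the curves would also shift; the documents do not say whether it does.

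**Working it through.** **The plan's own figure.** The plan gives no cumulative incidence and no competing-death rate. Its one reproducible design figure is the sample size in protocol 10.1: "by one year will be 30% in patients with multiple 18F-fluoride positive plaques, and 20% in other patients, we need 692 (231+461) subjects". With p1 = 0.30, p2 = 0.20, allocation k = 2, two-sided 5% and 80% power:

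- pooled p = (0.30 + 2 × 0.20)/3 = 0.2333
- uncorrected n = [1.960 × √(1.5 × 0.2333 × 0.7667) + 0.8416 × √(0.21 + 0.16/2)]² / 0.1² = 215.7
- corrected n = (215.7/4) × [1 + √(1 + 6/(215.7 × 2 × 0.1))]² = 230.4

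This gives 231 and 2 × 230.4 = 460.8, so 461, total 692. It reproduces, and nothing below changes it.

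**Formulas for the excess.** With constant event hazard l and competing-death hazard m per year:

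- 1 − KM = 1 − exp(−l t)
- cumulative incidence = l/(l + m) × [1 − exp(−(l + m) t)]

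**Inputs.** All rates are assumptions. Protocol 4.3 excludes "Major intercurrent illness with life expectancy <2 year", which supports including low death rates. The range for MI and revascularisation goes higher because cardiac deaths compete there too.

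Example, primary, l = 0.07, m = 0.03, t = 4: 1 − exp(−0.28) = 24.42%; 0.7 × [1 − exp(−0.40)] = 23.08%; excess 1.34 points.

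| Endpoint (l per year) | m per year | Excess at 2 years (points) | Excess at 4 years (points) |
|---|---|---|---|
| Primary (0.07) | 0.01 / 0.02 / 0.03 | 0.13 / 0.25 / 0.38 | 0.46 / 0.91 / 1.34 |
| MI or revascularisation (0.04) | 0.01 / 0.03 / 0.06 | 0.08 / 0.22 / 0.44 | 0.28 / 0.83 / 1.60 |
| Cardiac death (0.02) | 0.01 / 0.02 / 0.03 | 0.04 / 0.08 / 0.11 | 0.15 / 0.30 / 0.44 |

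**High-rate anchor.** The protocol's 20% one-year planning risk is for death or recurrent MI, so it already contains non-cardiac deaths. The total hazard is −ln(0.8) = 0.2231, and the competing part should come out of it:

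- m = 0.01, l = 0.2131: excess 0.32 points at 2 years and 0.97 at 4.
- m = 0.05, l = 0.1731: excess 1.34 points at 2 years (29.27% against 27.93%) and 4.16 at 4 (49.97% against 45.81%).

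Treating the whole 20% as event hazard and adding m = 0.05 on top would give 1.61 and 4.74, which counts those deaths twice.

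**Sampling error for comparison.** Greenwood half-width = 1.96 × S(t) × √(∫₀ᵗ l / [n exp(−(l + m)u) G(u)] du). G(u) = 1 to 2 years and then (6 − u)/4, that is, follow-up spread evenly over 2 to 6 years; m = 0.025. At 4 years:

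- l = 0.07, n = 231: 6.3 points.
- Difference between groups, l = 0.105 with n = 231 against l = 0.07 with n = 461: 8.3 points.

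The 231 and 461 are the planning split, which was based on multiple positive plaques and not on CMA status.

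**Gap between curves.** With an assumed hazard ratio of 1.5 (0.105 against 0.07), 1 − KM gives a gap of 9.87 points at 4 years. The true gap is:

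| Non-cardiac death per year | True gap | Gap from 1 − KM is |
|---|---|---|
| 1% in both groups | 9.70 | 0.17 too wide |
| 3% in both groups | 9.38 | 0.49 too wide |
| 3% with CMA, 2% without | 8.94 | 0.93 too wide |
| 2% with CMA, 3% without | 9.97 | 0.10 too narrow |

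**Direction.** In 300 simulated cohorts of 700 with 2 to 6 years of follow-up, one minus Kaplan-Meier was never below the Aalen-Johansen estimate at any time, apart from rounding.

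**The case against.** The strongest reply is that no planned conclusion changes. The log-rank test and the Cox model, with competing deaths censored, are valid comparisons of cause-specific hazards and do not use the plotted curve. The SAP names the estimator and states the censoring rule beside each figure, so a careful reader can tell what is plotted. It plans no tabulated Kaplan-Meier percentages at fixed times and no risk difference; the tabulated absolute quantities are counts and N (%), which are correct. At realistic rates the excess is well inside the sampling error. Every size quoted rests on rates that the documents do not give.

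Most of this stands, and it is why the point is minor. It does not remove the point. A confidence interval conveys sampling error; it does not convey an error that always runs in one direction and, at these constant rates, is larger at 4 years than at 2. A figure labelled cumulative incidence invites readers to take risks off it at chosen times, and no other planned output gives them. The planned all-cause and cardiac death results bound the number of competing deaths but do not show how many came before the event, so a reader cannot make the exact correction.

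**Conclusion.** The concern holds as a minor reporting correction. Four figures (SAP 5.3.2, 5.4.2, 5.4.3 and 5.4.4) would sit at or above the quantity they name. That direction follows from the estimator and needs no assumption about rates.

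The size does need assumptions: constant hazards and assumed event and death rates. On the moderate assumptions for the primary endpoint the overstatement is 0.1 to 0.4 points at 2 years and 0.5 to 1.3 at 4 years. At the high-rate anchor, with competing deaths taken out of the 20%, it reaches about 1.3 and 4.2 points. The moderate figures are well below the 4-year half-width of about 6.3 points.

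The primary inference, the hazard ratios, the sample size, the N (%) tables and the all-cause death figure are not affected.

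**What to change.** - In the four figures, plot Aalen-Johansen cumulative incidence by CMA status. The competing event is non-cardiac death for the primary composite and for cardiac death, and any death for non-fatal MI and unscheduled revascularisation.
- Add one table of competing deaths occurring before the event, by CMA status.
- Keep the log-rank and Cox analyses, and describe the hazard ratios for these four endpoints as cause-specific.
- Keep Kaplan-Meier for all-cause death.
- Because protocol 10.2.2 names Kaplan-Meier, that curve can stay beside the new one, labelled as one minus Kaplan-Meier with competing deaths censored.
- At minimum, remove the cumulative-incidence label from the four figures.

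No new data are needed, since all-cause and cardiac death are already endpoints. The minimum version edits four figure specifications; the full version adds the curves and one small table. Protocol 10.2.2 and its copy in SAP section 2 need no change if the Kaplan-Meier curve is kept and relabelled.

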5.3.3 Exploratory analyses of primary outcome

Relationship between CMA, as a continuous measure of ¹⁸F-fluoride uptake, and the risk of suffering a primary outcome event will be explored using a Cox proportional hazards regression model with (transformed) CMA as the only explanatory variable. A range of potential transformations of CMA will be explored, including fractional polynomials, to find an optimal fit to the data.

A second Cox regression model with (transformed) GRACE score as the only explanatory variable will be used to explore the relationship between this risk score and the primary outcome. A range of potential transformations of GRACE score will be explored to find an optimal fit to the data. The precise version of the GRACE score used, and any necessary details of calculation, will be specified in the statistical report.

A third Cox regression model with both GRACE score and CMA as explanatory variables, transformed where appropriate, will be used to assess the incremental prognostic value of CMA over and above a conventional clinical risk marker.

Table: Hazard ratio of primary outcome for each explanatory variable, with 95% CI, and associated pvalue from each Cox regression model. Also for each model the C-statistic, with 95% CI, as a measure of the discriminatory ability.

5.4 Secondary endpoints

5.4.1 All-cause death

Table: N (%) of participants with all cause death by CMA status and overall.

Figure: Kaplan-Meier estimates of cumulative incidence from analysis of time from study entry to death by CMA status with p-value using a log-rank test. Participants who do not have a relevant outcome event will be censored at the time of last follow-up.

Table: Hazard ratio of all cause death by CMA status, with 95% CI, and associated p-value using Cox regression.

5.4.2 Cardiac death

Table: N (%) of participants with cardiac death by CMA status and overall.

Figure: Kaplan-Meier estimates of cumulative incidence from analysis of time from study entry to cardiac death by CMA status with p-value using a log-rank test. Participants who do not have a relevant outcome event will be censored at the time of non-cardiac death or last follow-up.

Table: Hazard ratio of cardiac death by CMA status, with 95% CI, and associated p-value using Cox regression.

5.4.3 Non-fatal recurrent myocardial infarction

Table: N (%) of participants with non-fatal recurrent myocardial infarction by CMA status and overall.

Figure: Kaplan-Meier estimates of cumulative incidence from analysis of time from study entry to first non-fatal recurrent MI by CMA status with p-value using a log-rank test. Participants who do not have a relevant outcome event will be censored at the time of death or last follow-up.

Table: Hazard ratio of non-fatal recurrent myocardial infarction by CMA status, with 95% CI, and associated p-value using Cox regression.

5.4.4 Unscheduled coronary revascularisation

Table: N (%) of participants with unscheduled coronary revascularisation by CMA status and overall.

Figure: Kaplan-Meier estimates of cumulative incidence from analysis of time from study entry to first unscheduled coronary revascularisation by CMA status with p-value using a log-rank test. Participants who do not have a relevant outcome event will be censored at the time of death or last follow-up.

Table: Hazard ratio of unscheduled coronary revascularisation by CMA status, with 95% CI, and associated p-value using Cox regression.

5.5 Safety analyses

5.5.1 To determine the radiation exposure and effective dose associated with ¹⁸F-fluoride positron emission tomography and computed tomography coronary angiography

The following will be presented for the scanned population. Details of radiation exposure for patients in the safety population who are not in the scanned population will be put in a footnote.

Table: mean, standard deviation, median, lower and upper quartile, minimum, and maximum of injected ¹⁸F-fluoride activity (MBq) and effective radiation dose (mSv) from administration of radioactive tracer at baseline visit. The effective radiation dose (mSv) will be calculated from the administered dose using the conversion factor of 0.024 mSv/MBq. Mean, standard deviation, median, lower and upper quartile, minimum, and maximum of dose-length product (Gy·cm) and effective radiation dose (mSv) from computed tomography component of the scans at baseline visit. The effective radiation dose (mSv) will be calculated from the dose-length product using the conversion factor of 0.014 mSv/Gy·cm. Mean standard deviation, median, lower and upper quartile, minimum, and maximum of total effective radiation dose (mSv) at baseline visit.

The following will be presented for the participants who had a CT scan at 2 years.

Table: mean, standard deviation, median, lower and upper quartile, minimum, and maximum of dose-length product (mGy·cm) and effective radiation dose (mSv) from the scans at 2-year visit. The effective radiation dose (mSv) will be calculated from the dose-length product using the conversion factor of 0.014 mSv/Gy·cm.

These tabulations will not be split by CMA status.

5.5.2. To identify adverse events associated with ¹⁸F-fluoride positron emission tomography and computed tomography angiography

The following will be presented for the safety population.

Table: summary of adverse events within 48 hours of baseline visit showing both numbers and percentages of patients with events, and number of events. Also present these numbers split by whether events are serious or non-serious, and within seriousness by (i) causality (unrelated or possibly related for IMP and NIMP) and MedDRA preferred term (or an alternative classification), and (ii) MedDRA system organ class and MedDRA preferred term (or an alternative classification). No formal statistical analysis will be performed.

Listings with details of each serious adverse event and each non-serious adverse event, separately for those within 48 hours of baseline visit and 48 hours of 2-year visit.

These tabulations and listings will not be split by CMA status.

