7.2.4 Positron Emission and Computed Tomography Coronary Angiography

Patients may receive oral and/or intravenous beta-blockade, such as metoprolol 5-100 mg, to slow the heart rate to below 65 beats per minute to maximise image quality and reduce radiation exposure. Glyceryl trinitrate spray or tablet will be administered sublingually (200-400 µg) to induce coronary vasodilatation to enhance image quality of the coronary angiogram.

All patients will undergo dual cardiac and respiratory-gated positron emission and computed tomography imaging of the coronary arteries. Study subjects will be administered a target dose of 250 MBq ¹⁸F-fluoride intravenously and subsequently rested in a quiet environment for 60 min. An attenuation correction computed tomography scan will then be performed, followed by positron emission tomography imaging of the thorax in list-mode for 30 min. Computed tomography coronary calcium scan and angiography will be undertaken in the same visit as the ¹⁸F-fluoride scan and again at 2 years. An electrocardiogram-gated breath-hold computed tomography scan of the coronary arteries will be performed. A bolus of contrast (BMI adjusted) will be injected intravenously after determining the appropriate trigger delay with a test bolus. Because the use of contrast is required for the CT scan study participants may require pre-procedural check of estimated glomerular filtration rate (eGFR) according to local study site imaging protocols. If, however, a participant develops a contraindication to the contrast agent prior to the 2-year computed tomography calcium scan, the computed tomography calcium scan can be performed without contrast.

The positron emission tomography scans will be reconstructed in multiple phases of the cardiac cycle, with the diastolic phase (50-75%) used for analysis. Additional reconstructions will be undertaken as necessary. Positron emission tomography scans will correct for cardiac motion correction using electrocardiogram-gated images.

Further technical details of the specific CT-PET scanning procedures and how inter-site imaging standardisation will be achieved will be described in a separate scanning document.

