13.6.2 Risks

There are some potential hazards of the non-invasive investigations that we will perform as part of the trial. The main issues relate to exposure to ionising radiation and contrast agent administration. We have a well-developed protocol for cardiac positron emission and computed tomography imaging that minimises radiation exposure and has clear procedures for managing adverse contrast reactions. We anticipate that the total research protocol dose (TPRD) radiation exposure not exceed 34 mSv. The TRPD includes radiation exposure from both the positron emission tomography and computed tomography scans combined. The estimated associated risk of developing fatal cancer is proportional to dose. Using a risk of 5% per Sv [ARSAC Notes] in a healthy

population in this age group the estimated associated risk of developing fatal cancer as a result of this exposure is in the region 1 in 650. This risk can be classified as moderate. It is likely that in a population of any patients in the age group 50+ the cancer risk is lower than 5% per Sv. For comparison the average annual background radiation dose arising from natural sources of ionising radiation in the environment in the UK is 2.2 mSv. The TRPD of 34 mSv incurred in this study is approximately 15 times annual background radiation from natural sources. This can be compared with other commonly used cardiovascular imaging techniques, such as nucleotide myocardial perfusion imaging (15-20 mSv) and diagnostic coronary angiography (7 mSv) [Einstein *et al*, 2007].

The risks of exposure to the contrast medium include allergic reactions and impairment of kidney function. Amongst patients with moderate-to-severe chronic kidney disease, there is a 2-4% risk of kidney impairment after computed tomography angiography [Barrett *et al*, 2006]. The risk of contrast exposure in this study will be minimised by exclusion of high-risk patients who have significant kidney disease (estimated glomerular filtration rate <30 mL/min/1.73m²).

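### SAP 5.5.1 labels CT dose-length product Gy·cm at baseline and mGy·cm at 2 years, but converts both with one factor, 0.014 mSv/Gy·cm, and states no rescaling.

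*Combined protocol and SAP*

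**What the plan says.** SAP 5.5.1 plans two sets of radiation tables.

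- **Baseline.** It summarises "dose-length product (Gy·cm) and effective radiation dose (mSv) from computed tomography component of the scans at baseline visit", then the total effective dose at that visit (tracer plus CT).
- **2 years.** It summarises "dose-length product (mGy·cm) and effective radiation dose (mSv) from the scans at 2-year visit".

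The same rule follows each: effective dose "will be calculated from the dose-length product using the conversion factor of 0.014 mSv/Gy·cm". The section gives no conversion between Gy·cm and mGy·cm. The tracer part of the dose has its own rule, "using the conversion factor of 0.024 mSv/MBq".

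Protocol 2.1.3 makes radiation exposure and effective dose a safety objective, and 2.2.3 makes dose-length product and effective dose a safety endpoint. Protocol 7.1 says both quantities will be recorded for the baseline and 2-year scans. None of these sections gives a unit for dose-length product, and neither document gives a source for the factor 0.014.

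**The concern.** One numeric factor cannot be multiplied into two columns whose units differ by 1000. The baseline sentence is dimensionally consistent on its own. The 2-year sentence is consistent only if the analyst first divides by 1000, a step the SAP does not state. So at least one label is wrong, or a conversion step is missing.

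Two competent programmers could follow this text and report CT doses that differ 1000-fold. What is at stake is the CT part of a stated safety endpoint, and the baseline total to which it contributes. SAP section 6 reserves separate programming by a second statistician for the primary outcome. These tables get only the general read-through and sense-check of the report.

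**Working it through.** There is no stated result to reproduce: the factor is given without derivation, and the documents contain no dose-length-product values and no CT-only dose. The check is therefore one of units, followed by one of scale.

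**Units.** Let D be the true dose-length product of a scan in mGy·cm, so that it is D/1000 in Gy·cm. There are three ways to carry out the SAP's rule:

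- (a) Units honoured as written, with 2-year values divided by 1000 first: 0.014 × D/1000 at both visits.
- (b) Values held as labelled and multiplied directly: 0.014 × D/1000 at baseline and 0.014 × D at 2 years. The ratio is exactly 1000 for the same scan.
- (c) Values held in mGy·cm at both visits and multiplied directly: 0.014 × D at both visits.

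Whether each is right depends on the unit in which the factor is truly expressed:

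| Procedure | Factor truly per Gy·cm | Factor truly per mGy·cm |
|---|---|---|
| (a) | both visits right | both visits 1000-fold too low |
| (b) | baseline right, 2 years 1000-fold too high | baseline 1000-fold too low, 2 years right |
| (c) | both visits 1000-fold too high | both visits right; only labels wrong |

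Procedure (b) is wrong at one visit whichever unit is true. For (a) and (c), the answer turns on facts that the documents do not give: the factor's source and the stored unit.

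**Scale.** Inputs:

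- Tracer activity: participants are "administered a target dose of 250 MBq" (protocol 7.2.4).
- Tracer factor: 0.024 mSv/MBq (SAP 5.5.1).
- Ceiling for PET and CT combined: "radiation exposure not exceed 34 mSv" (protocol 13.6.2).

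With one tracer injection, as in the main study:

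1. Tracer dose: 250 × 0.024 = 6 mSv.
2. Most that CT can contribute under the ceiling: 34 − 6 = 28 mSv, over all main-study CT.
3. Dose-length product that would fill it: 28 / 0.014 = 2,000, in whatever unit the factor carries. That is 2,000 Gy·cm (2,000,000 mGy·cm) if the factor is per Gy·cm, or 2,000 mGy·cm if it is per mGy·cm.
4. If the factor is meant per mGy·cm but the units are honoured as written, 2,000 mGy·cm gives 0.014 × 2,000/1000 = 0.028 mSv instead of 28 mSv.
5. Set against the tracer, 0.028 / 6 = 0.5%. In that case CT all but disappears from the baseline total, even if all the CT dose the ceiling allows were delivered at baseline.

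The 28 mSv cannot be divided between visits from the documents. The baseline visit includes an extra CT acquisition ("An attenuation correction computed tomography scan will then be performed"), and no dose is given for any CT component.

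**The case against.** **The factor carries a unit, so a careful analyst would convert.** This is fair. A quantity shown in mGy·cm can be converted with a factor per Gy·cm by dividing by 1000, so the 2-year sentence is better called incomplete or inconsistently labelled than impossible. But the SAP is the programming specification, and it is silent on the step.

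**It may be a dropped letter.** Possibly. However, the form without the m appears three times in the section (the baseline label and both statements of the factor), and the form with it once. If it is a slip, the correction is the same.

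**An error this large would be noticed.** It may be. The report is to be sense-checked, dose-length product is tabulated beside effective dose, and the effective dose recorded under protocol 7.1 offers a direct comparison. These safeguards lower the severity but do not supply the missing unit.

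**A reader might go further and infer that the factor must be per mGy·cm.** The scale check can make 2,000 Gy·cm look implausible, and the protocol slows heart rate partly to "maximise image quality and reduce radiation exposure", which suggests that CT dose is regarded as material. Neither settles the unit. Choosing between 2,000 Gy·cm and 2,000 mGy·cm requires a typical dose-length product for these scans, and the documents give none. For the same reason they do not support a numerical estimate of how far the reported doses would be out in practice. Nor can one say that the baseline table is right because its sentence is consistent: that also depends on the values being stored in Gy·cm.

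**Conclusion.** The inconsistency stands: two dose-length-product units, one factor and no stated conversion. Its possible size is exactly 1000-fold in CT effective dose, at one visit or both. In the mildest case, with values stored in mGy·cm and a factor per mGy·cm, direct multiplication gives the correct mSv and only the labels are wrong.

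High confidence applies to the mismatch alone. Any statement about the direction of the error is conditional on the factor's true unit and the stored unit, both unknown here. The scale figures assume the target activity, a single tracer injection and a CT contribution at the limit of the 34 mSv ceiling; they are not expected doses.

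The affected tables are descriptive, untested and not split by CMA status. No primary or secondary analysis uses them. Severity is minor.

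**What to change.** In SAP 5.5.1:

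1. Use one unit for dose-length product in both tables.
2. Verify the unit of 0.014 against the factor's source, cite that source, and state the factor in the table's unit at both places. The choice matters: 0.014 mSv per mGy·cm equals 0.014 × 1000 = 14 mSv per Gy·cm, whereas 0.014 mSv per Gy·cm equals 0.014 / 1000 = 0.000014 mSv per mGy·cm.
3. Confirm the unit in which the database holds dose-length product at each visit before converting, and write down any rescaling step.
4. Compare the calculated doses with the effective doses recorded under protocol 7.1.

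The cost is a wording change in one section, one look-up of the factor's source and the database specification, and a simple comparison. No new data are needed.
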